7.1 Statistical Analysis

The analyses will be undertaken on statistical software (PRISM) and will compare the two groups. Rates of complications and outcomes will be reported descriptively. Data integrity will be checked by two researchers and inputted contemporaneously. Each researcher will be trained in outcome measures prior to study initiation.

We anticipate approximately 50% of participants will be unable to complete questionnaires due to confusion / low GCS etc. This is exploratory and if this is the case then these outcome measures will not be taken forward in the next stages of future trials. Otherwise we anticipate very few missing data in terms of the primary outcome measures and the objectively measured secondary outcomes due to the fact that we will have a researchers based on the neurosurgical units throughout the recruitment and intervention periods collecting and recording data.

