13.	Taking the Work Forward	. 20
14.	Intellectual Property (IP)	. 20
15.	Costing Schedule	. 21
16.	Funding Arrangements	. 21
17.	References	21

1. Study Synopsis/Profile

Study title	Investigating the tolerability and feasibility of transcutaneous vagus nerve stimulation following aneurysmal subarachnoid haemorrhage				
Study short title	tVNS in aSAH				
Study design	Two-arm randomised controlled trial				
Study participants	Inclusion criteria:				
	 Age >18 Admitted to STH neurosurgery Confirmed aneurysmal SAH on vascular imaging Within 5 days of 'Securing' aneurysm (i.e., successfully coiled or surgically following rupture) 				
	Exclusion criteria:				
	 Current or prior use of a vagus nerve stimulation Symptomatic bradycardia or PPM insertion Complete heart block Implantation of any other electrical stimulator (e.g. DBS) 				
Planned sample size	30 participants (15 in each arm)				
Planned study period	36 months				
Planned recruitment period	24 months				
Study assessments	 Deliver TVNS using the parasym device for 45 minutes twice daily for 5 days following aSAH intervention (coiling or clipping) Pulse width 25ms, frequency device standard (25 Hz), at maximum tolerated intensity, or 				

	20MA for patients who cannot report the maximum tolerated intensity • Clinical follow-up on discharge and at 1 month				
Objectives	s Primary				
•	To establish the tolerability, and feasibility of tVNS in patients following aSAH, including;				
	 Monitor tolerability for tVNS Symptom severity scores of mild or moderate in less than 1/3 of participants able to report symptoms Assess study feasibility recruit >1 patient per month of recruitment >80% of recruited patients completing primary outcome measures 				
	Secondary				
	 Monitor safety criteria for tVNS No SAEs reported to tVNS Unexpected AEs in less than 1/3 of participants Explore clinical outcomes including: rates of clinical or radiological DCI inpatient mortality inpatient length of stay Rate of complications: seizures, hyponatraemia, rebleed, hydrocephalus Outcome measures using questionnaires on discharge and at 1-month Disability assessment: modified Rankin Score, Barthel Index Assess frequency and severity of headache: Likert scale Explore mechanisms of action: Inflammatory markers at baseline and 5 days Explore response to tVNS: 				
	 Near-infrared cerebral spectroscopy Heart rate variability Pupillary reactivity 				

2. Research Questions

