6.7 Outcome Measures

Primary Outcome Measures – success criteria:

- Monitor tolerability for tVNS
 - Symptom severity scores of mild or moderate in less than 1/3 of participants able to report symptoms (based on Likert Scale 1-5; 1 representing no issues; 5 representing severe symptoms)
- Assess study feasibility
 - recruit >1 patient per month of recruitment
 - >80% of recruited patients completing primary outcome measures at 4 weeks follow up

These outcome measures will be collected during the participants inpatient stay over the intervention period using a data collection proforma (appendix) and taken from recruitment records kept contemporaneously. Safety assessment of SAEs / AEs will be collected each intervention day by our research team.

Secondary Outcome Measures:

- Monitor safety criteria for tVNS
 - No SAEs reported to tVNS
 - Unexpected AEs in less than 1/3 of participants
- Explore clinical outcomes including:
 - rates of clinical or radiological DCI (%)
 - inpatient mortality (%)
 - inpatient length of stay (days)
 - rate of complications: seizures, hyponatraemia, rebleed, hydrocephalus (%)
- Outcome measures using questionnaires on discharge and at 1-month
 - Disability assessment: modified Rankin Score, Barthel Index
 - Assess frequency and severity of headache: Likert scale
- Explore mechanisms of action:
 - Inflammatory markers at baseline and 5 days
- o Explore response to tVNS:
 - Near-infrared cerebral spectroscopy
 - Heart rate variability
 - Pupillary reactivity

These will be measured during the inpatient hospital stay up until discharge (Figure 1).

- Outcome measures using questionnaires at on discharge and at 4 week follow-up
 - Disability assessment: modified Rankin Score, Barthel Index
 - Assess frequency and severity of headache: Likert scale (1-10 where 1 is non-existent and 10 is extremely severe)
- Explore mechanisms of action measured at baseline and at the end of intervention (5 days):
 - Inflammatory marker analysis at baseline and 5 days (IL-1B, IL-6, IL-10, TNFa)
 - Concurrent WCC, CRP and infection will be recorded at these time points as these may confound results
- o Explore response to tVNS:
 - Near-infrared cerebral spectroscopy

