6.10 Study Protocol

Patients (or their representatives if they lack capacity) who are eligible for entry into the will be approached by the treating clinical teams with information about the study. Those who are interested will be given an information sheet and time to consider the study. Those keen to participate will sign a consent form (or assent form for those that lack capacity) and baseline outcome measures will be performed.

Enrolled participants will be issued with a study number and randomised 2:1 (SealedEnvelope Ltd) stratified according to age (<65 and ≥ 65 years). They will then receive either active tVNS stimulation (tragus) or sham (earlobe), twice daily for 45 minutes per session for 5 days. We do not anticipate discharges from hospital earlier than 5 days as this is not routine practice in the neurosurgical unit.

Primary outcome measures of tolerability and feasibility will be collected daily by researchers delivering the intervention, and secondary outcome measures will be collected at the end of intervention or on hospital discharge as detailed in figure 2.

Following discharge from hospital participants will return for follow up clinic assessment at 4 weeks where questionnaire measures of functional recovery and adverse event reporting will be undertaken. After this the participants involvement in the study will be complete.

Figure 2: Study Schedule for Outcome Measures

	Baseline visit	Visit 1	Visit 2	Visit 3	Visit 4	Visit 5 (EOT)	discharge	At 4 weeks
Eligibility screening	Х							
Informed consent	Х							
Randomisation	Х							
Socio- demographic data	X							
Clinical data collection	X						X	
Questionnaires: Disability - mRS, BI, headache likert scale	X						X	X
Reporting of side effects, adverse events and tolerability		X	X	X	X		X	X
Intervention reporting – settings delivered, duration of intervention		X	X	X	X			
Pupillometry + recording of prescribed eye drops	X					X		
Heart rate variability	X					X		
fNIRS	Х					X		
Monitor blood test results (secondary outcome measures), collection of data on WCC/CRP and infection status	Х	X	X	X	X		X	
Inflammatory marker analysis	X					Х		

EOT = End of treatment; BI = Barthel Index;

fNIRS = Functional near infra-red spectroscopy

7. Data Management

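### mRS and Barthel are grouped with the headache questionnaire, so expected non-completion by confused or low-GCS patients would leave disability unscored in about half and drop it from future trials

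*Protocol*

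**What the plan says.** Protocol 6.7 lists, under "Outcome measures using questionnaires on discharge and at 1-month", the item "Disability assessment: modified Rankin Score, Barthel Index" and, beside it, the headache Likert scale. The schedule in Figure 2 (section 6.10) puts all three in one row, "Questionnaires: Disability - mRS, BI, headache likert scale", marked at baseline, discharge and 4 weeks. The text of 6.10 also describes functional recovery at the 4-week clinic visit as a questionnaire measure.

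Section 7.1 then treats questionnaires as a block: "We anticipate approximately 50% of participants will be unable to complete questionnaires due to confusion / low GCS etc". The consequence follows at once: "if this is the case then these outcome measures will not be taken forward in the next stages of future trials". The next sentence sets the other outcomes apart: "Otherwise we anticipate very few missing data in terms of the primary outcome measures and the objectively measured secondary outcomes". No exception is made for mRS or Barthel.

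Two other statements bear on the point. Section 7.1 says "Each researcher will be trained in outcome measures prior to study initiation" and places researchers on the neurosurgical units throughout recruitment and intervention. Section 10.1 justifies enrolling patients who lack capacity on the ground that their inclusion is critical to generalisability.

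**The concern.** Confusion or a low GCS stops a patient from rating their own headache. It need not stop a trained rater from scoring dependence. That mRS and Barthel can be scored by an observer or from a proxy is general knowledge of the instruments, not a statement in the protocol. The protocol nevertheless puts them under the same expected non-completion, and the same consequence, as a symptom scale that only the patient can answer.

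Two things are at stake:

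- **The pilot's own description of disability.** The stated reason for non-completion is neurological state, so the participants left with scores would tend to be the better ones. Section 10.1 makes a point of enrolling patients without capacity; section 7.1 then expects no questionnaire data from many of them.
- **The choice of endpoint for the next trial.** Section 13 plans a larger trial of whether tVNS improves outcomes after SAH. The trigger for setting the measures aside is the rate the protocol itself expects, so the rule would probably apply. Functional outcome would then be lost because of its mode of collection, not its performance.

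**Working it through.** The protocol derives no figure here. The 50% is its own expectation and has no stated inputs, so there is nothing to reproduce. The arithmetic shows only what follows from it.

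**Inputs**

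- Planned total: 30 (Synopsis; section 6.5 says at least 30). The split between arms is not needed.
- Expected non-completion: m = 0.5 (section 7.1). No time point is given; it is applied here to whichever assessment it holds for.
- Poor-outcome rates: not in the documents. Assumed at 20% in completers and 50% to 80% in non-completers.
- Poor-outcome proportion for the precision and bounds illustrations: assumed 30%.

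**Step 1: number scored.** 30 × (1 − 0.5) = 15.

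**Step 2: precision.** Interval width scales with 1/√n, so the ratio is √(30/15) = 1.41. At an assumed 30% poor outcome, the normal-approximation 95% half-width is 1.96 × √(0.3 × 0.7 / n):

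- n = 30: 0.164, about 16 points
- n = 15: 0.232, about 23 points

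**Step 3: error in the overall level.** The rate in all participants is 0.5 × p(completers) + 0.5 × p(non-completers). The completers alone show p(completers). The understatement is therefore 0.5 × [p(non-completers) − p(completers)].

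| Completers | Non-completers | All participants | Understatement |
|---|---|---|---|
| 20% | 50% | 0.5 × 20 + 0.5 × 50 = 35% | 15 points |
| 20% | 80% | 0.5 × 20 + 0.5 × 80 = 50% | 30 points |
| 30% | 30% | 30% | 0 |

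**Step 4: bounds without assuming a rate in the missing half.** If 30% of the scored half have a poor outcome, the rate in all participants lies between 0.5 × 30% = 15% (none of the missing) and 0.5 × 30% + 50% = 65% (all of the missing).

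**Step 5: after the change.** If both scales are scored by a researcher from the patient or a proxy, up to 30 of 30 can have a score. The half-width returns to about 16 points and the severity-related gap largely closes. The headache scale stays limited to patients able to report.

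**The case against.** The strongest reply is that self-completion is never stated. Section 6.7 speaks of a disability assessment, 6.10 of a clinic assessment at 4 weeks, and 7.1 of researchers trained in the outcome measures. All of this fits researcher-scored scales. The data collection proforma that 6.7 mentions is not in the text at hand and may settle the mode. This stands as a limit: self-completion is inferred from the reason given for non-completion. It does not remove the point. If rater scoring was always meant, then 6.7, 7.1 and Figure 2 misdescribe it, and the same edit is needed.

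It can also be said that rating source and coding of deaths belong in an analysis plan or scoring manual. That is fair for the detail. But the protocol itself fixes the classification and the rule on future trials, and no analysis plan can recover scores that were never taken.

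Four stronger readings are tempting and are not supported:

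- **That the comparison between arms would be biased.** This needs missingness that differs by arm, or treatment that changes who can respond. The protocol gives no evidence of either. What follows is distortion of the overall level and loss of precision.
- **That the pilot itself abandons the scales.** The rule concerns later trials only; here they are still collected. It is also conditional, and section 7.2 says further statistical advice would be sought for a future study.
- **That the same half is missing throughout.** Section 7.1 gives no time point, and ability to respond may differ between baseline, discharge and 4 weeks.
- **That the primary completion criterion of more than 80% is threatened.** That criterion concerns the primary outcome measures, for which 7.1 expects few missing data. mRS and Barthel are secondary.

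Finally, these are exploratory secondary outcomes in a pilot that section 7.2 acknowledges is not powered for them. Wider intervals alone would change no decision in this trial.

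**Conclusion.** The point holds in limited form. As written, the protocol classes two disability scales as questionnaires, expects about half of participants to be unable to complete questionnaires for reasons tied to neurological state, and makes that the ground for not using the measures again. Followed literally, about 15 of 30 participants would have disability scores and intervals would be about 1.41 times wider. The overall disability level would look better than it is by 15 to 30 points under the assumed rates, and by nothing if completers and non-completers are alike.

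The conclusion rests on the protocol's own 50%, on the inference that patients would complete the scales themselves, and on assumed outcome rates that only illustrate size. The link between confusion or low GCS and worse disability is plausible, but the protocol does not state it.

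The main consequence is for the next trial's endpoint, which is one of the things a pilot should inform. The change is worth making before data collection. It does not bear on the tolerability and feasibility criteria.

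**What to change.** In Protocol 6.7, 7.1 and Figure 2:

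- List mRS and Barthel separately from the headache self-report, and give Figure 2 two rows.
- State that the trained researchers score both scales for every participant at each scheduled time, from the patient, a carer, ward staff or records, and note the source.
- Score deaths as mRS 6, and state how deaths are handled on the Barthel Index.
- Limit the rule about future trials to patient-reported headache, and confine the 50% expectation in 7.1 to that measure.

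The cost is a wording change and a carer contact at 4 weeks for participants who cannot answer, within the work of the existing researchers. Proxy ratings are somewhat noisier than direct ones; recording the source lets the report show how far results depend on it.

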7.2 Statistical Opinion

This is a pilot study which hopes to form the basis of further grant funding for a larger study. This is a provisional study to demonstrate tolerability and feasibility. Further statistical advice would be sought should further funding be granted for future study. Primary outcome data will be reported descriptively (proportions, %).

Continuous data will be compared using parametric or non-parametric analyses depending on whether data distribution is normal or not. Categorical data will be compared using Chi-square or one-way ANOVA. However, due to the small sample size, appropriate power to detect significant differences for these measures will not be reached. This is primarily an exploratory study and most data will be reported descriptively.

Between group differences in baseline characteristics will be compared using parametric (T-Tests) and non-parametric (Mann – Whitney U, Chi squared) tests, depending on normality of distribution.

A secondary outcome of this study is safety of TVNS in patients who have suffered a subarachnoid haemorrhage. Utilising the definition of SAE, if no SAE's are reported which are deemed related to tVNS by the research team, then we can be 95% confident that the true SAE rate lies between 0 and 12%.¹⁵

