Is transcutaneous nerve stimulation a tolerable and feasible intervention to potentially improve clinical outcomes in aneurysmal subarachnoid haemorrhage (aSAH)?

3. Abstract/Summary

Background

Subarachnoid haemorrhage (SAH) is a type of brain bleed, which can be complicated by issues including delayed cerebral ischaemia (DCI) which causes stroke like symptoms, such as weakness, in up to 30% of patients. Current treatments for DCI focus on improving blood supply but fail to address other important factors including reducing inflammation.

Stimulation of a nerve in the neck called the vagus nerve, which can be done through the skin (transcutaneous vagus nerve stimulation, tVNS) is known to relax blood vessels and reduce inflammation and is approved in other conditions such as epilepsy.^{3,4} In animals, vagus nerve stimulation improves survival after aSAH, and is being studied in humans to reduce headaches after aSAH.^{5,6}

There is a theoretical role of tVNS in improving outcome after aSAH. We aim to study whether tVNS is tolerated, and feasible in aSAH.

Methods

This is a single centre, pilot randomised controlled trial (RCT); the participants will receive either tVNS or 'sham' tVNS, twice daily for 45 minutes for 5 days. We will monitor tolerability (symptoms) and feasibility (recruitment rates) for recruited patients. Secondary outcomes will include rates of side effects, complications from SAH, outcomes on discharge and 4 week follow up, and exploration of mechanisms of action and response to tVNS including levels of serum inflammatory markers (IL-1B, IL-4, IL-6, IL-10 and TNFa), functional near infra-red spectroscopy (f-NIRS), heart rate variability (HRV) and pupillary light reactivity (PLR).

Results

Rates of complications, side effects and recruitment will be reported descriptively and we will undertake simple between-group statistical analyses on secondary outcome measures. If proven to be tolerated and feasible, this study will provide the basis for a future larger trial design.

4. Aims of the Study

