6.9 Intervention

We are using tVNS settings that are widely used in other neurological conditions (epilepsy, migraine)¹⁴. These include:

- o Pulse width 25ms
- Frequency device default (20 or 25Hz)
- Intensity below pain threshold.
- Frequency 45 minutes twice daily. On the basis of similarity to other studies, practicalities on the ward and clinical scenario

We have chosen a duration of 5 days based on the usual clinical pathway of inpatient management at the Royal Hallamshire Hospital, and have chosen to deliver the treatment twice daily to optimise the dose. This is a pilot study with feasibility outcomes and as such we will be exploring the feasibility of this treatment regimen.

The Parasym Device will be applied to the left tragus (figure 1) as this is the most common site for tVNS delivery in neurological studies and is associated with few afferents to the heart.

The intervention is aimed at supplementing routine clinical care, and as such, the doses of tVNS can be interrupted for care activities (therapy sessions, examinations, assessments etc) and resume afterwards. The overall minute duration will aim to remain 45 minutes twice daily.

[figure not shown]

Figure 1. Anatomy of the ear and the tragus (a). Parasym attached to the tragus (b)

The active intervention will be compared to sham tVNS where the vagal nerve stimulator will be attached to the earlobe instead of the tragus, in keeping with evidence that this does not cause vagus nerve stimulation and is in line with sham methods used in other studies. We do not anticipate that patients will have the intervention long enough to become familiar with the common sensations associated with true tVNS intervention. At the end of the intervention period, participants will be asked if they thought they had received true of sham tVNS to understand the blinding ability of the sham.

We will use the FNIRS Lumo ecosystem (Gower labs) to assess cerebral blood flow in the frontal lobes. We will complete a protocol where 6 optodes are placed bilaterally over the frontal and prefrontal cortices. We will complete and record resting state signals of oxyhaemoglobin and deoxyhaemoglobin for 5 minutes while patients are layed in bed with their eyes closed (or wearing an eye patch). Following the 5-minute rest phase, vagal nerve stimulation or sham stimulation will start

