depending on the participants randomisation and signal acquisition will continue for 5 minutes. After this time, the stimulation will cease and a further 5 minutes of resting signal acquisition will be completed. The data acquired during this protocol will undergo processing (adjustment for background and physiological noise) and data analysis using recommended software (Homer 2/3). Data analysis will look to compare signal acquisition between resting and stimulation states and will evaluate any lasting effects of stimulation following termination. We will perform this on the first and last day of the intervention, before and after stimulation respectively.

We will be using Reflex Pupillometry to measure pupillograms in response to a light stimulus during an intervention session for all participants. This will be done at a different time to the Lumo FNIRS assessment. Recording of the pupillary response will follow the following protocol; 3 baseline measures taken 1 minute apart prior to stimulation will represent baseline pupillograms (which will be averaged). Following this, stimulation (active or sham) will start and 3 times pupillograms will be measured at 1 minute intervals following initiation. After completion of the treatment session, 3 further pupillograms separated by 1-minute intervals will be measured - that will constitute the recovery phase. We acknowledge that environmental influences (ambient light intensity, equipment noise and administered medications may confound pupillography, however this analysis is exploratory.

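### Section 7.2 names one-way ANOVA for categorical data, commits to significance tests of baseline characteristics, and points to unadjusted comparisons where ANCOVA on baseline inflammatory markers and HRV could be more precise (minor)

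*Protocol*

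**What the plan says.** Section 7.2 (Statistical Opinion) states three rules for comparing the arms.

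- Categorical outcomes: "Categorical data will be compared using Chi-square or one-way ANOVA".
- Continuous outcomes: "Continuous data will be compared using parametric or non-parametric analyses depending on whether data distribution is normal or not".
- Baseline table: "Between group differences in baseline characteristics will be compared using parametric (T-Tests) and non-parametric" tests, the latter given as Mann-Whitney U and chi-squared.

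The abstract (section 3) describes the same plan: "we will undertake simple between-group statistical analyses on secondary outcome measures". No baseline-adjusted analysis is named anywhere.

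The data for such an analysis are nevertheless scheduled. Section 6.7 lists "Inflammatory marker analysis at baseline and 5 days", and Figure 2 marks inflammatory markers and HRV at the baseline visit and at end of treatment. Randomisation is "stratified according to age" at 65 years (section 6.10).

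The protocol also limits what rests on these comparisons. Section 7.2 says that primary outcomes are reported descriptively, that the secondary comparisons lack power, and that the study is mainly exploratory.

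**The concern.** There are three separate weaknesses.

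1. One-way ANOVA tests equality of means. A category has no mean unless codes are assigned to it, so the method does not belong in a sentence about categorical data.
2. Under randomisation, any baseline difference between the arms is due to chance. A significance test of that difference asks a question whose answer is known, and with several variables it is likely to flag something.
3. A comparison that ignores a measured baseline discards information. Section 4 wants early signals of effect, and section 13 wants data to support a grant application. At 30 patients the useful output is an estimate with its interval, as narrow as the collected data allow.

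At stake are correct wording and some precision in the exploratory results, not the trial's conclusions on tolerability or feasibility.

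**Working it through.** The protocol gives no power or precision figure for these outcomes, so there is none to reproduce.

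**Inputs.** N = 30 (synopsis, section 6.5). The synopsis gives 15 per arm and section 6.10 gives 2:1 randomisation. That conflict is a separate matter, so both 15/15 and 20/10 were used. Two-sided 5% level: assumed. Baseline-outcome correlation rho: not given, so 0 to 0.7 is shown. N = 24 complete pairs (20% loss): assumed.

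**1. ANOVA on binary data.** With X² the uncorrected chi-square statistic, one-way ANOVA on 0/1 data gives F = (N − 2)X² / (N − X²).

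- Chi-square rejects at X² > 3.84. ANOVA rejects at F(1, 28) > 4.196, which is X² > 30 × 4.196 / (28 + 4.196) = 3.91.
- The two can differ only if X² falls between 3.84 and 3.91. Enumerating every table, 0 of 256 (15/15) and 0 of 231 (20/10) do.
- Exact size at a 30% event rate is therefore the same for both tests: 5.5% at 15/15 and 4.7% at 20/10.

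With three unordered levels the result would depend on coding. An invented table (6, 3, 6) v (3, 9, 3) gives ANOVA p = 1.00 with codes 1, 2, 3 and p = 0.0499 with codes 1, 3, 2; chi-square gives 5.0 on 2 df, p = 0.082. The protocol names no such outcome.

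**2. Baseline tests.** With k independent tests at 5% under valid randomisation, the chance of at least one significant difference is 1 − 0.95^k: 23% for k = 5, 40% for k = 10, 54% for k = 15.

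**3. ANCOVA on the baseline value and age stratum (k = 2 covariates).** The ratios of the ANCOVA standard error to that of the simple comparison are:

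- against day-5 values: sqrt[(1 − rho²)(1 + k/(N − k − 3))];
- against change scores: the same, with the variance divided by 2(1 − rho).

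For N = 30 the second factor is 1 + 2/25 = 1.08; for N = 24 it is 1 + 2/19 = 1.105.

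| rho | v day-5, N = 30 | v change, N = 30 | v day-5, N = 24 | v change, N = 24 |
|---|---|---|---|---|
| 0 | 1.039 | 0.735 | 1.051 | 0.743 |
| 0.1 | 1.034 | 0.771 | 1.046 | 0.780 |
| 0.2 | 1.018 | 0.805 | 1.030 | 0.814 |
| 0.3 | 0.991 | 0.838 | 1.003 | 0.848 |
| 0.5 | 0.900 | 0.900 | 0.910 | 0.910 |
| 0.7 | 0.742 | 0.958 | 0.751 | 0.969 |

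Example: rho = 0.5, N = 30: sqrt(0.75 × 1.08) = sqrt(0.81) = 0.900.

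Break-even against day-5 values is rho = sqrt(1 − 1/1.08) = 0.27 at N = 30 and sqrt(1 − 1/1.105) = 0.31 at N = 24.

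A simulation of 20,000 runs per case, with the age stratum balanced by design, gave 0.97 to 0.98, 0.89 and 0.73 against day-5 values at rho 0.3, 0.5 and 0.7, for both splits. The formula is therefore slightly cautious.

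**Validity of the stated route.** Choosing between t-test and Mann-Whitney by a normality test gave a simulated type I error of 5.2% (normal data) and 4.6% (lognormal data) at 20/10. ANCOVA on the baseline value alone gave 4.8 to 5.0% in a separate simulation.

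**The case against.** The strongest reply concerns the third part. Section 7.2 names no test for continuous outcomes; the t-test and Mann-Whitney U appear only in the baseline sentence. ANCOVA is a parametric analysis, so it is not excluded, and a statistical analysis plan may specify it. This stands as a limit: the text points to simple comparisons, mainly through the abstract's wording, but does not rule out adjustment. The third part is therefore a cheap improvement, not a demonstrated error.

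The gain is also assumed. Below a correlation of about 0.27, ANCOVA is slightly less precise than day-5 values, and section 6.7 itself warns that infection may confound the markers. This stands, and is why the whole range is shown.

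A reader might want the same ANCOVA for fNIRS and pupillometry, which also have a baseline visit in Figure 2. The protocol does not support that. Section 6.9 already sets out within-session comparisons: for fNIRS, "record resting state signals of oxyhaemoglobin and deoxyhaemoglobin for 5 minutes", then stimulation, then rest again, with rest compared to stimulation; for pupillometry, "3 baseline measures taken 1 minute apart prior to stimulation will represent baseline pupillograms", then stimulation and recovery readings. The pre-stimulation reading is already the reference, and ANCOVA on a first-day baseline could replace the stated response measure with a different one.

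A reader might also infer that naming ANOVA, or choosing tests by normality, makes the results invalid. The calculations show otherwise: binary decisions do not change, and error rates stay near 5%. The baseline tests feed no analysis or success criterion, so they too change no planned result.

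**Conclusion.** The point holds and is minor. Two parts rest on the text alone: ANOVA is misnamed for categorical data, and baseline significance tests are uninformative under randomisation. Neither alters a planned result.

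The third part is an available gain in precision for inflammatory markers and HRV. Against day-5 values at N = 30, the standard error is 1%, 10% or 26% smaller at rho 0.3, 0.5 or 0.7, and 2 to 4% larger at rho 0 to 0.2. If the simple comparison were of change scores, ANCOVA is more precise at every correlation computed (0 to 0.7). These figures assume a roughly linear relation on the analysis scale and a correlation the protocol does not give. There is no baseline-adjustment gain for DCI, mortality, length of stay or complications, which have no baseline value.

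The outcomes are exploratory, no success criterion in section 6.7 depends on them, and validity is not affected.

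**What to change.** In section 7.2:

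1. Remove one-way ANOVA from the sentence on categorical data.
2. Replace the baseline significance tests with descriptive summaries by arm.
3. For inflammatory markers and HRV, report the arm difference at end of treatment with a 95% confidence interval, from ANCOVA on the baseline value and age stratum. Use the log scale for the markers and for skewed HRV measures (LF power, HF power, LF/HF ratio).
4. Leave fNIRS and pupillometry to the within-session comparisons in section 6.9.

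No new data are needed, and the first two changes are wording only. The third costs two degrees of freedom per model, can lose a few per cent of precision against day-5 values if the correlation is low, and needs software that fits a linear model with covariates. The team should confirm that the package named in section 7.1 does so.
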